9.3.6 Assessment of routine laboratory measurements (day 1-7)

Laboratory assessments at start and during treatment will be part of the clinical routine. Either on the day before or on the day of study treatment start, participants will receive routine blood sampling which includes blood count (Hb, Tc, Lc), measurement of renal function (creatinine) and liver function (ALT, gGT), as well as inflammatory parameter (CRP). The study team will review the blood samples at start and during treatment and will re-order any missing laboratory measurements from the collected blood samples if, in rare cases, the necessary measurements for the study according to the visit plan were not routinely performed. No additional blood should be drawn to assess clinical routine measurements. The blood count should be measured 4 times between day 1 (-1) and day 7 (± 1), creatinine and CRP at least on day 1 and day 5 (± 1), creatinine also on day 14 (± 3) if a participant is still hospitalised.

9.3.7 Subproject *Molecular mechanisms of S. aureus bacteraemia* (day 1 until 48h after the patient's first negative blood culture)

Only for a subgroup of patients included in Basel, Switzerland.

Blood will be used to determine the location of *S. aureus* in the blood (intra- or extracellular).

For this, a maximum of one additional 7.5 ml EDTA tube of blood per day will be collected from day 1 until follow-up blood cultures remain negative for 48 hours.

- For patients who consented to further analysis of *S. aureus* in their blood, blood samples will be collected daily. If no routine blood work is performed on an eligible day, an additional blood draw should be performed to collect the sample.
- For patients enrolled via the confirmation of an independent physician under emergency exception from informed consent requirements, blood samples will only be collected during routine blood drawing.
- For patients who refused consent to further analysis in the blood, no additional blood samples for the subproject will be taken.

9.3.8 Follow-up blood cultures (day 2, day 5 ± 1)

Follow-up blood cultures are routinely performed and repeated in *S. aureus* bacteraemia until blood cultures become negative. This belongs to the guidelines-supported management of such infections. At day 2 after trial enrolment one further pair of blood culture should be drawn. This needs to be ordered by the treating physician. If the prior blood cultures were still positive for *S. aureus*, then these follow-up blood cultures will be routinely ordered and drawn. If the prior blood cultures were negative, then the blood cultures at day 2 need to be ordered additionally to the clinical routine. If day 2 blood culture stayed positive, then further follow-up cultures are mandated at day 5 (± 1) and will be part of the clinical routine as outlined above.

9.3.9 Assessment of SIRS criteria (day 5 ± 1)

The components of the SIRS criteria (abnormal body temperature, mechanical ventilation, tachycardia, and abnormal leucocytes) are routinely assessed and documented during clinical management of the hospitalised participants. The vital parameters (body temperatures, respiratory rate, pulse) are usually measured at least once daily. Leukocytes are usually measured every 1-3 days. Tachypnoea is assessed when clinically indicated. Thus, these criteria will be collected from the hospital information system data.

9.3.10 Measurement of trough levels of linezolid in a subset of participants (day 4-5)

Participating centres will collect one 7.5 ml Monovette® Li-Heparin from participants between day 4 and 5 after randomisation for a representative linezolid trough measurement. Plasma sampling may be combined with the routine blood draw but should be timed immediately before the next linezolid dose.

Plasma should be isolated by centrifugation and frozen as soon as possible after blood draw, but at the latest within 6 hours. Samples will be stored at -80°C until shipment. Periodically, samples are shipped on dry ice to the University Hospital Basel where linezolid trough levels will be analysed by the diagnostic laboratory.

9.3.11 Assessment of adverse events of special interest (day 1-5, day 14 ±3, discharge day)

- Clinical signs of serotonin toxicity until day 7: Serotonin toxicity will be assessed during clinical routine. Participants will routinely be visited daily by the treating physician. Daily measurement of vital signs including blood pressure is part of the clinical routine. In case of clinical signs of serotonin toxicity, the Hunter criteria and diagnostic algorithm will be used (including spontaneous or inducible clonus, ocular clonus, tremor, hypertonia and hyperthermia, agitation or diaphoresis, hyperreflexia). In case of clinical signs of serotonin toxicity, the IMP administration will be halted. The local investigator will be involved to re-assess the clinical picture and to confirm or reject the observation. The local investigator will then decide if the participant can continue taking the IMP or needs to stop the intervention.
- Laboratory signs of myelosuppression until day 7: Participants will be monitored for signs of myelosuppression (thrombocytopenia, anaemia, leukopenia) as part of the clinical routine blood sampling. If blood count shows signs of myelosuppression, the local investigator will be involved to assess the potential causality between the IMP and the laboratory measurements. The local investigator will then decide if the participant needs to stop the intervention.
- Evidence of hyperlactatemia until day 7: In case of a clinical suspicion of hyperlactatemia, the local investigators must collect a blood sample to assess if the lactate level is above the upper norm according to specific laboratory-defined reference ranges. For increased lactate levels, the causality with the study treatment will be assessed. The local investigator will then decide if the participant needs to stop the intervention.
- Acute kidney injury: the kidney function is measured in the blood (creatinine) regularly as part of the clinical routine. To collect this outcome, the serum creatinine at baseline, on day 5 (± 1), and only if participant remains hospitalised, at day 14 (± 3 days) will be documented. The values will be captured from available data from the hospital information system.
- *C. difficile*-associated diarrhoea within 90 days: The treating clinicians will assess for *C. difficile* infection based on the centre-specific diagnostic algorithm if clinical suspicion arises due to diarrhoea during antibiotic treatment. *C. difficile* infection will be evaluated on day 14, at discharge, and on day 90 by reviewing the participant's electronic health records. If a participant reports severe diarrhoea during a 90-day follow-up phone call, occurring after discharge and managed outside the centre, the responsible physician may be contacted to determine if a *C. difficile* infection was diagnosed.

9.3.12 Assessment of serious adverse events and serious adverse reactions (from enrolment until discharge, and at day 90 ±7)

All assessments of serious adverse events (SAE) and serious adverse reactions (SAR) during acute care hospitalisation will be part of the routine clinical work-up and monitoring of the participants. This generally includes a daily routine visit and evaluation of the participant by the treating physician. Further, the vital signs (blood pressure, pulse, body temperature, oxygenation) will be measured regularly by the nursing staff. Blood samples will regularly be taken to measure organ function (myelopoiesis, liver, kidney). For severely ill participants treated on the intensive-care unit, the clinical as well as laboratory evaluation is generally much more frequent. Any serious adverse event will be reported to the study-site principal investigator, who then assesses whether there is a reasonable causal relationship with the IMP. Assessment will take place from enrolment until acute care hospital discharge. Further, any post-discharge occurrence of an SAE/SAR will be assessed during the phone call at day 90 follow-up.

9.3.13 Assessment of new antibiotic resistance (discharge day)

Any *S. aureus* detected at a new site of infection in a participant will routinely be tested for its antibiotic susceptibility as part of the clinical microbiological work-up and according to the respective standards of the responsible laboratory. In case of persistent or repetitive detection of *S. aureus* in the blood, the microbiological laboratory will decide if an antibiotic susceptibility testing should be repeated. Detection of any new resistance not present in the *S. aureus* from the initial blood culture will count as new antibiotic resistance. The standard susceptibility testing suffices; additional determination of the MIC of an antibiotic is not necessary except if clinically indicated. The data will be gathered from the hospital information system.

9.3.14 Assessment of microbiological failure (day 28, discharge day, day 90 ±7)

“Early microbiological failure” and “microbiological failure” are defined as the identification of any new focus of *S. aureus* between 5 and 13 days, or 14 and 90 days after randomisation, respectively. This will be assessed by reviewing the participant’s microbiological results in the electronic health records. Any detection of *S. aureus* (by culture or by culture-independent methods such PCR) within the time frame will be further investigated in detail by reviewing the corresponding clinical health records. Thereby it can be determined – if necessary - whether the *S. aureus* originated from a sterile site. Any change of the initial antibiotic (and/or surgical) treatment plan will be analysed if it occurred due to proven detection of *S. aureus* at a sterile site. During the 90-day telephone call, it will be asked if any microbiological samples were taken outside of the corresponding centre. If this is the case, the responsible laboratory will be directly contacted to ask to provide the corresponding results. The principal investigator of each site will finally decide if a microbiological failure occurred. Furthermore, the independent outcome assessment board will review each documented microbiological failure on a case-by-case basis.

9.3.15 Assessment of clinical failure (day 14, day 28, discharge day, day 90)

“Early clinical failure” and “clinical failure” are defined as the identification of any new focus of *S. aureus* between 5 and 13 days, or 14 and 90 days after randomisation, respectively. This encompasses not only microbiological findings (i.e. detection of *S. aureus*) but also clinical, radiological and histological results. Clinical failure will be assessed by screening of patient history on multiple levels in the available electronic health records and during the telephone call at day 90: any change of the initial antibiotic (and/or surgical) treatment plan will be analysed if it occurred due to proven or assumed new focus of *S. aureus*. Further, all available microbiological results, histological results as well as radiological exams will be screened for signs of newly identified *S. aureus* focus/foci. In case of ambiguous interpretations, the treating physicians can be contacted directly to inquire his/her interpretation of the results. The principal investigator of each site will finally decide if a clinical failure occurred. Furthermore, a blinded panel of experts, selected by the trial investigators, will review each documented clinical failure on a case-by-case basis.

9.3.16 Assessment of length of hospital stay and length of ICU stay (discharge day)

At the time of acute care hospital discharge, the length of hospital stay will be documented according to the hospital records. Similarly, length of stay on the ICU will be extracted from the electronic hospital records.

9.3.17 Assessment of all-cause mortality (day 7, day 14, day 28, day 90 ±7)

The data will be examined in both the hospital records and, when available, external documents to ascertain whether the participant has died during the follow-up period. If the participant cannot be reached for the 90-day telephone follow-up, their emergency contact or primary care physician will be contacted. Documentation of the presumed cause of death is not mandatory.

9.3.18 Assessment of return to usual level of function (day 90 ±7)

During the phone call at day 90, the participant will be asked to rate their level of function in the 4 weeks prior to their bacteraemia and their current level of function from 6 to 1 according to the modified functional bloodstream infection score (see chapter 5.1 *Primary Outcome* for the corresponding scale). All levels of the scale will be presented orally in a clear and precise manner, ensuring that the participant has adequate time to self-assess. In the event of any misunderstanding regarding the classifications, the scale will be repeated as necessary. If the participant is unable to perform the self-assessment (whether due to medical reasons or limited communication abilities over the phone), efforts will be made to contact a family member or the participant’s primary care physician to obtain the information.

9.3.19 Assessment of physical and mental health (quality of life, SF-36, day 90 ±7)

Quality of life (i.e. mental health and physical health) will be assessed at day 90 through the SF-36 questionnaire. Participants will have the option to complete it either electronically or on paper. At the time of enrolment in the study, participants will be asked which method they prefer. For the electronic version, participants will be requested to provide their email address and/or mobile phone number. This information will be encrypted and accessible only to the local Investigator of the respective centre. On day 90, participants will be notified via email or mobile phone

message about the task and will be directed to the corresponding online version of the study-specific SF-36 questionnaire. For participants who prefer the written version, a letter with a printed version of the SF-36 questionnaire will be sent by postal mail, including an envelope for returning the filled questionnaire. We expect that participants will need approximately 10 minutes to complete the questionnaire. At the time of the 90-day telephone call, participants will be asked whether they have already completed the questionnaire and if they have any questions regarding it. It is not intended for the questionnaire to be filled out verbally over the phone, as this could potentially introduce bias.

10. SAFETY

10.1 Drug studies

During the entire duration of the study, all serious adverse events (SAEs) are collected, fully investigated and documented in source documents and case report forms (CRF). Predefined adverse events of special interest (AE) critical to the safety evaluation will be assessed as outlined in the study protocol. Study duration encompasses the time from when the participant signs the informed consent form until the last protocol-specific procedure has been completed, including a safety follow-up period.

10.1.1 Definition and assessment of (serious) adverse events and other safety related events

An **Adverse Event (AE)** is any untoward medical occurrence in a patient or a clinical investigation participant administered a pharmaceutical product and which does not necessarily have a causal relationship with the study procedure. An AE can therefore be any unfavourable and unintended sign (including an abnormal laboratory finding), symptom, or disease temporally associated with the use of an investigational medicinal product, whether or not related to the investigational medicinal product. [ICH E6 1.2]

A **Serious Adverse Event (SAE)** is classified as any untoward medical occurrence that:

- results in death,
- is life-threatening,
- requires in-patient hospitalization or prolongation of existing hospitalisation,
- results in persistent or significant disability/incapacity, or
- is a congenital anomaly/birth defect.

In addition, important medical events that may not be immediately life-threatening or result in death, or require hospitalisation, but may jeopardise the patient or may require intervention to prevent one of the other outcomes listed above should also usually be considered serious. [ICH E2A]

SAEs should be followed until resolution or stabilisation. Participants with ongoing SAEs at study termination (including safety follow-up visit) will be further followed up until recovery or until stabilisation of the disease after termination.

Assessment of Causality

Both Investigator and Sponsor make a causality assessment of the event to the study investigational medicine product, based on the criteria listed in the ICH E2A guidelines:

Relationship	Description
Definitely	Temporal relationship Improvement after de-challenge* Recurrence after re-challenge (or other proof of drug cause)
Probably	Temporal relationship Improvement after de-challenge No other cause evident
Possibly	Temporal relationship Other cause possible
Unlikely	Any assessable reaction that does not fulfil the above conditions
Not related	Causal relationship can be ruled out

*Improvement after de-challenge only taken into consideration if applicable to reaction

Unexpected Adverse Drug Reaction

An “unexpected” adverse drug reaction is an adverse reaction, the nature or severity of which is not consistent with the applicable product information (e.g. Investigator’s Brochure for drugs that are not yet approved and Product Information for approved drugs, respectively). [ICH E2A]

Suspected Unexpected Serious Adverse Reactions (SUSARs)

The Sponsor evaluates the SAE that has been reported regarding seriousness, causality and expectedness. If the event is related to the investigational medicinal product and is both serious and unexpected, it is classified as a SUSAR.

Assessment of Severity

Severity of any AEs will be graded by the local Investigator as well as the Sponsor-Investigator based on the following criteria according to the Common Terminology Criteria for Adverse Events (CTCAE) Version 5.0 published November 27, 2017 ¹¹⁶.

Severity	Description
Grade 1	Mild; asymptomatic or mild symptoms; clinical or diagnostic observations only; intervention not indicated.
Grade 2	Moderate; minimal, local or non-invasive intervention indicated; limiting age-appropriate instrumental ADL*.
Grade 3	Severe or medically significant but not immediately life-threatening; hospitalization or prolongation of hospitalization indicated; disabling; limiting self care ADL**.
Grade 4	Life-threatening consequences; urgent intervention indicated.
Grade 5	Death related to AE.

A semi-colon indicates 'or' within the description of the grade. ADL: Activities of Daily Living

*Instrumental ADL refer to preparing meals, shopping for groceries or clothes, using the telephone, managing money, etc.

**Self care ADL refer to bathing, dressing and undressing, feeding self, using the toilet, taking medications, and not bedridden.

10.1.2 Reporting of serious adverse events (SAE) and other safety related events

Reporting of SAEs

All SAEs must be reported immediately and within a maximum of 24 hours of becoming aware of the SAE to the Sponsor-Investigator of the study. The Sponsor-Investigator will re-evaluate the SAE in a separate eCRF form and provide feedback to the site in case the Sponsor-Investigator's opinion differs. In addition, SAEs will also be evaluated during the interim analyses with the DSMB (including external clinical experts as well as patient and public representatives; see also chapter 11.4.4 *Interim analysis*).

Reporting of SUSARs

A SUSAR must be reported to the Ethics Committee (local event via local Investigator) via BASEC and to Swissmedic (via the Sponsor-Investigator) within 7 days of becoming aware of the SUSAR if the event is life-threatening or fatal. For all other SUSARs, the report must be made within 15 days.

The reporting obligations of SUSAR also apply if the investigator or the sponsor becomes aware of a suspected case after termination of the clinical trial.

Reporting of immediate safety and protective measures

All suspected new risks and relevant new aspects of known adverse reactions that require immediate safety-related measures, must be reported to the Sponsor-Investigator within 24 hours of becoming aware of the new risks. The Sponsor-Investigator must report these measures within 7 days to the Ethics Committee (local event via local Investigator) via BASEC and to Swissmedic.

The Sponsor must immediately inform all participating Investigators about the immediate safety and protective measures.

Reporting and Handling of Pregnancies

In the event of pregnancy, the treating physician and the participant (or the participant's next of kin) will determine

whether the potential benefits for the participant outweigh the potential risks to the foetus. The course and outcome of the pregnancy should be followed up carefully, and any abnormal outcome regarding the mother or the child must be documented and reported.

Periodic reporting of safety and general progress of the clinical trial.

Once a year, the Sponsor-Investigator submits to the CEC and Swissmedic a list of the safety events including the severity of the events, their causality to the intervention and the safety of the study participants. This report also includes an update on the general progress of the study.

The safety and general progress reports encompass the time from the date of the sponsor's first authorisation to conduct the clinical trial in any country worldwide until the Last Patient Last Visit in Switzerland.

The safety and general progress report is submitted yearly to the CEC and to Swissmedic throughout the duration of the clinical trial in Switzerland, and the last submission of the safety report will cover the Last Patient Last Visit in Switzerland.

10.1.3 Follow up of (Serious) Adverse Events

SAEs occurring during hospitalisation will be followed-up until they are resolved during the hospital stay. If any study personnel become aware of an SAE outside of hospital, the responsible local investigator must conduct regular follow-ups until the SAE is resolved. At least 5 attempts at different times of the day to reach the participant will be conducted by the treating physician (or a delegated physician). If these fail, reasonable attempt will be made to acquire the information from relatives, caregivers, or the participant's emergency contact or primary care physician.

10.2 Assessment, notification and reporting on the use of radiation sources

Not applicable.

10.3 Exemption from the documentation requirements of AE

10.3.1 Exemption from the documentation requirements of AE due to pharmacological arguments

Not applicable.

10.3.2 Exemption from the documentation requirements of AE due to clinical arguments

Not applicable.

11. STATISTICAL METHODS

11.1 Hypothesis

Primary research hypothesis: Inhibition of virulence factor expression by early 5-day treatment with linezolid (600 mg twice daily) in addition to treatment with standard antibiotics will result in superior outcomes at 90 days compared to placebo in participants with *S. aureus* bacteraemia.

11.2 Determination of Sample Size

We collected retrospective data on the DOOR components from all *S. aureus* bacteraemia patients treated at the University Hospital Basel in 2022 (n=119). Our assumptions for the sample size are based on these data along with what is known from the literature to derive plausible estimates for the DOOR components. Patients who died in the first three days after a *S. aureus* bacteraemia diagnosis were excluded so that we do not overestimate the mortality of the planned trial (of note, most of these patients would probably have died before they could have been included in our study ($n = 8$)). Following extensive consultations with patient representatives, we have established that, for mortality at 90 days, a trial should demonstrate a meaningful relative difference of 10% (equating to an absolute difference of 2.2%). Meanwhile, for the remaining domains, the following relative reductions were deemed acceptable: 15% for level of function and 20% for complications and length of hospital stay).

The sample size was calculated using a simulation approach, for which 1000 synthetic datasets for each combination of plausible values for the relevant parameters were generated. We calculated the p -value of the win ratio for each of the simulated datasets and tested for statistical significance at $\alpha = 0.05$ using the unmatched win-ratio approach described in Pocock et al.¹¹⁷. The final sample size is based on the following specific assumptions:

- The statistical tests are conducted at a two-sided significance level of $\alpha=0.05$, and the desired power is 90%
- The two treatment arms are equal in size (1:1 allocation)
- The proportion of deaths within 90 days in the control group is expected to be 22.5% and 20.3% in the linezolid group (relative reduction of 10%; absolute reduction of 2.2%)
- The proportion of participants with worse level of function in the control group is expected to be 25.0% ²¹, and 21.3% in the linezolid group (relative reduction of 15%; absolute reduction of 3.7%)
- The proportion of participants with any complications (defined DOOR component) will be 6.3% in the control group and 5.0% in the linezolid group (relative reduction of 20%; absolute reduction of 1.3%).
- We modelled hospital length of stay using a log-normal model with any of the complications listed in the definition above as an independent variable; the parameters for this model were derived from the retrospective USB data, and the expected 20% relative reduction in hospital length of stay due to the intervention was applied to the mean of the log-transformed data when generating synthetic datasets.
- Missing data were accounted for in the simulations (i.e., 10% for worse level of function and only 3% for all other components as these data will be available from routinely collected data). In case of missing DOOR components, the comparison among participants was made with the following DOOR domain.

Under the assumptions listed above, 550 participants are required to show a significant effect of the intervention. Since it is possible that some patients themselves or their next of kin withdraw consent post-randomisation, we increased the target sample size by 10% to minimise the risk of being underpowered. Hence, we plan to include 606 participants (303 participants in each study arm).

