Number of Participants with Rationale:	
606 participants (303 in control and 303 in the intervention group)
 
We will use the win ratio to assess if participants in the intervention group have a better overall clinical outcome as defined by the DOOR compared to participants in the control group taking the following domains into considerations: i) survival, ii) participant-reported level of functioning at 90 days compared to the level before the blood infection, iii) treatment change due to persistence or spread of the bacterium within day 14-90 or serious adverse events leading to study drug discontinuation, and iv) hospital length of stay in days.
 
The sample size was calculated using a simulation approach (including missing data in the assumptions), for which 1000 synthetic datasets for each combination of plausible values for the relevant parameters were generated and the intended primary analysis was applied. With a two-sided significance level of $\alpha=0.05$ and a desired power of 90% (1:1 allocation), an estimated 550 participants will be required to show a significant effect of the intervention. Because of possible post-randomisation withdrawal due to missing retrospective consent, the sample size was increased by 10% to minimise the risk of being underpowered.
 
See section 11 STATISTICAL METHODS for detailed assumptions about (i) occurrence of events and potential effect for each DOOR domain and (ii) about the frequency of missing data for each DOOR domain.

Study Duration:	
Estimated duration for the main investigational plan (e.g. from start of screening of first participant to last participant processed and finishing the study):
 
38 months

Study Schedule:	
First patient in: September 2025
 
Last patient out: October 2028

Local site- Investigators:	Please refer to the separate document "LIPS list of project leaders" for detailed information on local investigators.
Study Centres:	Approximately 12 institutions in Switzerland will be involved in this multi-centric trial. Please refer to the separate document "LIPS trial sites" for the complete list.
Statistical	Primary analysis:

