8.2 Administration of experimental and control interventions

8.2.1 Experimental Intervention

One linezolid 600 mg tablet will be administered orally twice a day on 5 consecutive days (chapter 3.4 *Clinical Evidence to Date*). For hospitalised participants, the study drug will be distributed in the same manner as a participant's other oral medication. The local investigator or delegated staff will hand over the study drug to the nursing team who will distribute the study drug to the participant according to the instructions by the physician and according to the site-specific local procedures. In general, each dose/each tablet will be distributed separately to the participant and only just before intake. If, based on the treating team's assessment, a participant is unable to swallow the study medication, tablets may be crushed and resuspended for easier consumption or for administration via a nasogastric tube according to clinical routine and following site-specific SOPs.

In the unlikely event that participants are discharged home before day 5, they will receive the remaining study medication along with detailed instructions on how and when to take them at home.

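### Was the 20% reduction in hospital stay put into the sample-size simulation as something other than a 20% cut in days?

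*Protocol*

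**What the plan says.** Protocol section 11.2 lists the relative reductions settled on after consultation with patient representatives: 10% for death, 15% for level of function, and "20% for complications and length of hospital stay". For death, function and complications it gives a proportion in each arm and both the relative and the absolute reduction; the complications entry, for instance, ends with "relative reduction of 20%; absolute reduction of 1.3" percentage points.

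Hospital stay is handled differently. It was drawn from a log-normal model with complications as an independent variable, and "the parameters for this model were derived from the retrospective USB data", meaning the 2022 Basel cohort. The section then says that "the expected 20% relative reduction in hospital length of stay due to the intervention was applied to the mean of the log-transformed data" when the synthetic datasets were generated. No log-mean, log-SD or stay in days is given for either arm.

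The section concludes: "Under the assumptions listed above, 550 participants are required to show a significant effect of the intervention". A 10% allowance for withdrawn consent takes this to 606. The synopsis repeats that "an estimated 550 participants will be required to show a significant effect of the intervention" and points to section 11 "for detailed assumptions about (i) occurrence of events and potential effect for each DOOR domain".

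**The concern.** A relative reduction in days and a relative reduction in the mean of log-days are different quantities. The sentence can be read as any of three operations on the control log-mean:

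- (a) add ln(0.8);
- (b) subtract 0.20;
- (c) multiply by 0.8.

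Reading (c) is what the words suggest if the reduction is taken to act on the log-mean itself, and it would be a far larger effect than the one agreed. With no stay parameters reported, a reader cannot repeat the simulation and see which was used.

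The stakes would be real. Stay breaks ties among survivors who match on function and complications, so it decides many pairs. If the simulation had used (c), 550 and 90% power would belong to roughly twice the agreed cut in stay. Power for the agreed 20% cut could then be well below 90%.

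**Working it through.** **Inputs from section 11.2.** Two-sided alpha 0.05; power 90%; 1:1 allocation, so 275 per arm at 550; death 22.5% v 20.3%; worse function 25.0% v 21.3%; complications 6.3% v 5.0%; missing data 10% for function and 3% for each other component, with the comparison then passing to the next domain; unmatched win ratio.

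**Inputs the protocol does not give, assumed here.** Control median stay 10, 15 or 20 days; log-SD varied; a complication lengthens stay by 0.3 on the log scale.

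**Figures that can be checked directly.** 22.5 × 0.90 = 20.25; 25.0 × 0.85 = 21.25; 6.3 × 0.80 = 5.04; 550 × 1.10 = 605, made even at 606. All agree with the protocol. The 550 cannot be reproduced or refuted from the stated inputs alone, because the stay parameters are missing.

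**Size of the cut in days under each reading.**

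- (a) 1 − exp(ln 0.8) = 20.0%, at any median.
- (b) 1 − exp(−0.20) = 18.1%, at any median.
- (c) 1 − median^(−0.2) = 36.9%, 41.8% and 45.1% at medians of 10, 15 and 20 days. It equals 20% only where the log-mean is 0.2231/0.2 = 1.116, a median of 3.05 days.

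**Simulated power at 550.** All-pairs win ratio, test of the log win ratio with a U-statistic variance, function proportions applied to survivors, 1,000 to 3,000 replicates per cell (Monte Carlo error 0.5 to 1.6 points).

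| Reading | Log-SD at which 550 gives 90% power |
|---|---|
| (a) | about 0.43 |
| (b) | about 0.39 |
| (c), median 10 / 15 / 20 days | about 0.89 / 1.05 / 1.16 |

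Near those points the win ratio is about 1.40 to 1.41 under every reading. For the agreed 20% cut, power at 550 over medians of 10 to 20 days is:

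| Log-SD | 0.40 | 0.45 | 0.50 | 0.6 | 0.8 | 1.0 |
|---|---|---|---|---|---|---|
| Power | 92% | 88% | 82–84% | 75–77% | 57–60% | 50–51% |

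With no effect on stay (median 15 days, log-SD 0.8), the win ratio is 1.10 and power 15.8%. Stay decides about 36% of pairs. So the input matters, and everything turns on which operation and which log-SD were used.

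**What the protocol says about the operation.** Both sentences in section 11.2 attach the 20% to hospital stay, not to its logarithm. In a log-normal model a proportional change in days enters as a shift in the log-mean, so the sentence reads naturally as saying where the effect was entered. Only (a) gives exactly 20% in days. Reading (c) is not a 20% reduction in stay at realistic medians, and its size would change if stay were measured in hours.

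**A cross-check on spread.** Section 8.2.1 treats early discharge as exceptional: "In the unlikely event that participants are discharged home before day 5". Section 8.9 also calls discharge before the course is complete rare. The share of controls staying under 4 days is Φ(ln(4/median)/log-SD):

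- Where (c) gives about 90% power: 15.4% (median 10, log-SD 0.90), 10.4% (15, 1.05), 8.1% (20, 1.15).
- Where (a) is close to 90% (log-SD 0.45): 2.1%, 0.2% and 0.02% at medians 10, 15 and 20.

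This favours (a) with a narrow spread. The protocol gives no percentage, so it does not prove it.

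**Is a log-SD near 0.43 credible?** Section 8.7 describes targeted treatment for at least 2 to 6 weeks, mostly intravenous. As an illustration only, if 80% of stays lay between 14 and 42 days, the log-SD would be ln(3)/2.563 = 0.43. Outpatient parenteral treatment and rehabilitation days do not count as stay (section 5.1), so this is no estimate, but it shows that the value is not excluded. The spread in the model is also the residual one after conditioning on complications.

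**The case for a change.** The strongest case for acting is that section 11.2 is the protocol's own sample-size justification, that the synopsis sends the reader there for the effect in each domain, and that the domain carrying most of the effect is the only one with no value in either arm. If the log-SD were 0.6 to 1.0, a true 20% cut would have only about 50% to 77% power at 550. Settling the matter would take a look at one line of code.

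Part of this stands. The reporting is thinner for stay than for the other domains, and a reader cannot verify 550. But the low power figures need log-SDs that no part of the protocol supports, and the 37% to 45% cuts need both assumed medians and a coding slip that nothing in the text demonstrates. Reading (b) hardly matters: 18.1% instead of 20% moves the matching log-SD only from 0.43 to 0.39. Checking the code would be reasonable housekeeping, but it would alter the plan only if it exposed an error for which there is no evidence.

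**Conclusion.** The concern does not hold as a fault in the plan. The protocol states a 20% reduction in hospital stay and says at which point of a log-normal model it was entered. The ordinary way of doing that, adding ln(0.8) to the log-mean, gives exactly the stated effect and is consistent with 550 and 90% power at a log-SD of about 0.43 to 0.45. That log-SD is assumed, since the protocol neither states nor excludes it, and the power figures also rest on the assumed medians and complication shift. The alternative that would matter, multiplying the log-mean by 0.8, fits the wording of the agreed effect poorly and sits less well with early discharge being rare.

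What remains is missing simulation detail: the operation, the control log-mean, the log-SD and the implied win ratio. A statistician holding the Basel data and the code has these to hand. The target of 606, the win-ratio analysis and its interpretation are unaffected, so no change follows.
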